### **3.5 Subject Demographics and Pre-Treatment Characteristics**

Subject demographics will be summarized for the All Enrolled and Full Analysis Set – Cervical Mucus populations. Pre-treatment characteristics will be summarized for the All Enrolled population. The demographics and pre-treatment characteristics will be summarized for all subjects.

#### **3.5.1 Demographics**

The summary of demographics will include age, race, ethnicity, weight and height at screening and BMI. The summary will be done for the All Enrolled and FAS Cervical Mucus populations and will include:

- The number and percentage of subjects within each category of race and ethnicity.
- The sample size, mean, median, SD, minimum, and maximum values for age, weight, height and BMI. Age will be calculated (with the INTCK function) using the Screening Visit Date and the Date of Birth.

#### **3.5.2 Contraceptive History**

The number and percentage of subjects reporting contraceptive history for each contraceptive method will be summarized. For those subjects not at risk of pregnancy, the reasons why not at risk will also be summarized.

#### **3.5.3 Gynecological History**

The summary of gynecological history will include average cycle length, usual flow duration, heaviest volume of flow, history of irregular periods, yeast infection history and bacterial vaginosis history. The summary will include:

- The number and percentage of subjects within each category of heaviest volume of flow, history of irregular periods, yeast infection history and bacterial vaginosis history.
- The sample size, mean, median, SD, minimum, and maximum values for average cycle length and usual flow duration.

### **3.5.4 Pregnancy History**

The summary of pregnancy history will summarize the following endpoints:

- The number and percentage of subjects within each category of complications during pregnancy, complications with baby, any pregnancy planned within the next 4 months and breastfeeding history and current status.
- The sample size, mean, median, SD, minimum, and maximum values for number of times pregnant and number of live births.

### **3.5.5 Substance Use History**

The summary of substance use will summarize the number and percentage of subjects for the following categories:

- Alcohol use
- Marijuana use
- Illicit drug use

The sample size, mean, median, SD, minimum, and maximum values quantify use of these substances will also be presented.

### **3.5.6 Physical Examination**

Physical examinations will be performed at screening. Each body system will be categorized as normal or abnormal. The number and percentage of subjects in each category will be given for each body system.

### **3.5.7 Gynecological Examination**

Gynecological examinations will be performed at screening. Each body system will be categorized as normal or abnormal. The number and percentage of subjects in each category will be given for each body system.

### **3.5.8 Gynecological Assessments**

The summary of gynecological assessments will summarize the number and percentage of subjects for the following categories:

- Chlamydia test type
- Chlamydia test results
- Chlamydia treated (positive test results only)
- Gonorrhea test type
- Gonorrhea test results
- Gonorrhea treated (positive test results only)
- Vaginitis test results
- Vaginosis test results
- Vaginosis treated (positive test results only)
- PAP smear required?
- PAP smear results

### **3.5.9 Medical History**

The number and percentage of subjects reporting a medical history for each body system will be summarized.

### **3.5.10 Pre-Treatment Signs and Symptoms**

Pre-treatment signs and symptoms will be coded using MedDRA 21.0. The number and percentage of subjects reporting each pre-treatment sign and symptom will be summarized by system organ class and preferred term for the Safety population. The number and percentage of subjects reporting any pre-treatment signs and symptoms will also be reported.

If a subject reports the same pre-treatment sign or symptom more than once, then that subject is only counted once for the summary of that pre-treatment sign or symptom, using the most severe intensity.

### **3.5.11 Prior and Concomitant Medications**

Summaries for prior and concomitant medications will be done for the Safety population. Each summary below will be done for all subjects:

- Prior Medications – Prior medications are considered to be any medication that was stopped prior to the date of the first dose of study drug.
- Concomitant Medications – Concomitant medications are considered to be any medication that was taken on or after the date of the first dose of study drug.

All medications recorded on the CRF will be coded to the therapeutic drug classes and generic drug names using the World Health Organization (WHO) Drug classifications. The WHO Drug dictionary version used for this study will be March 2018.

Each summary will give the number and percentage of subjects who took medications that were coded to each generic drug name and therapeutic drug class, as well as the number and percentage of subjects that took any medication at all. If the start or end date of the medication is a partial date (or completely unknown) then the medication will be classified as a concomitant medication unless the partial end date is clearly before the first dose of study drug.

### 3.5.12 Screening Transvaginal Ultrasound

The endometrial stripe thickness and endometrium appearance at the screening transvaginal ultrasounds will be summarized for all subjects using the Safety population.

## 3.6 Treatment Compliance

Compliance will be summarized for the Safety and FASM populations.

Compliance =  $100 * (\text{total \# pills indicated as taken on diary entries}) / (\text{date last pill taken} - \text{date first pill taken} + 1 - \text{number of planned missed doses})$ . The compliance calculation will be different for each treatment group, as based on treatment schedule. The reported perfect use period (treatment period 1) and the delayed pill period have 0 planned missed doses while the missed pill period has 1 planned miss dose.

The following information will be presented for each treatment group for compliance:

Summary statistics (sample size, mean, median, SD, minimum, and maximum) for treatment compliance

The number and percentage of subjects in each of the following categories of compliance: <75%, 75% - <85%, 85% - <95%, 95% - <100%, and 100%.

Compliance will also be summarized for the Safety population for treatment periods 1 and 2 combined as well as for all treatment periods combined.

## 3.7 Efficacy Analysis

All efficacy analyses will be done for the appropriate FAS, PP and ITT populations unless otherwise specified.

    - $TMS_{2B,R} = T_{2R-1} + 6 \text{ h} \pm 15 \text{ min}$  at **V2R**
    - $TMS_{3B,R} = T_{3R-1} + 3 \text{ h} \pm 15 \text{ min}$  at **V3R**
- Time of mucus scoring the day **after** infringement (both arms):
  - $TMS_{2R+1} = T_{2R-1} - 30 \text{ min}$  (before pill intake) at  $V_{2R+1}$  and
  - $TMS_{3R+1} = T_{3R-1} - 30 \text{ min}$  at  $V_{3R+1}$ .

The **time of pill intake** the day after infringement should be the same as the day before infringement (expected around 9 am).

The **primary baseline time points** are:

[figure not shown]
- $TMS_{2R-1} = T_{2R-1} + 8 \text{ h} \pm 30 \text{ min}$  at  $V_{2R-1}$  and
- $TMS_{3R-1} = T_{3R-1} + 8 \text{ h} \pm 30 \text{ min}$  at  $V_{3R-1}$

Around 8 hours after pill intake the day before infringement.

The **primary response time points** are:

- Arm A:
  - $TMS_{2A,R} = T_{2R-1} + 3 \text{ h} \pm 15 \text{ min}$  at  $V_{2R}$
  - $TMS_{2R+1} = T_{2R-1} - 30 \text{ min}$  (before pill intake) at  $V_{2R+1}$
  - $TMS_{3A,R} = T_{3R-1} + 6 \text{ h} \pm 15 \text{ min}$  at  $V_{3R}$
  - $TMS_{3R+1} = T_{3R-1} - 30 \text{ min}$  (before pill intake) at  $V_{3R+1}$
- Arm B
  - $TMS_{2B,R} = T_{2R-1} + 6 \text{ h} \pm 15 \text{ min}$  at  $V_{2R}$
  - $TMS_{2R+1} = T_{2R-1} - 30 \text{ min}$  (before pill intake) at  $V_{2R+1}$
  - $TMS_{3B,R} = T_{3R-1} + 3 \text{ h} \pm 15 \text{ min}$  at  $V_{3R}$
  - $TMS_{3R+1} = T_{3R-1} - 30 \text{ min}$  (before pill intake) at  $V_{3R+1}$ .

The **primary measures** of mucus are taken at the time presented in the following figure:

The **primary outcomes/endpoints** are the changes from baseline (BSL):

- Delta from BSL to  $V_{2R}$  = Mucus score at  $V_{2R}$  - score at  $V_{2R-1}$  (period 2): change from baseline to 3 or 6 hour after infringement
- Delta from BSL to  $V_{2R+1}$  = Mucus score at  $V_{2R+1}$  - score at  $V_{2R-1}$  (period 2): Change from baseline to just before pill intake the day after infringement
- Delta from BSL to  $V_{3R}$  = Mucus score at  $V_{3R}$  - score at  $V_{3R-1}$  (period 3) change from baseline to 3 or 6 hour after infringement
- Delta from BSL to  $V_{3R+1}$  = Score at  $V_{3R+1}$  - score at  $V_{3R-1}$  (period 3) Change from baseline to just before pill intake the day after infringement

The **primary model** of interest is a mixed model for repeated measures using as response delta to  $V_{2R}$ , delta to  $V_{2R+1}$ , delta to  $V_{3R}$  and delta to  $V_{3R+1}$ . The covariates will be the period (or period effect), the intervention (type of infringement: missed pill or delayed pill), the sequence of intervention (missed pill then delayed pill and vice versa), the time (visit) and the subject. Time, period intervention type, and sequence will be considered as categorical variables. The subject as random effect (RANDOM statement of the MIXED procedure). This will permit to take into account the fact that measures from each period are derived from the same subjects. A time repeated effect (REPEATED statement of the MIXED procedure) within each combination subject\* period (SUBJECT = subject\* period as option of the

REPEATED statement). This will permit to take into account the fact that for each subject, at each period several measures are performed over time. The proper structure of the variance covariance matrix will be retained using the best fit among unstructured matrix (UN) compound symmetry (CS) and autoregressive structure (AR1).

The **primary test of interest** will be the significance of the overall mean (intercept). This will answer the question: is the overall mean change from baseline different from zero? Or does the infringement of schedule regardless the type of infringement lead to a change in mucus score?

The **contrasts or estimates of interest** are

- The effect of infringement type: does the effect of missed pill differ from the effect of 6 hours delay? If the answer is yes, then a signal of effect is detected.
- The effect of time: does the response on the day of infringement differ from the response on the day after infringement? If the answer is yes, then a signal of effect of infringement is detected.

The **primary cut-off** for full cervical mucus protection is a cervical mucus score of 4. There is, therefore, a good conception protection by cervical mucus if the cervical mucus score is  $\leq 4$ . If the cervical mucus was too thick to be collected (and thus a cervical mucus score could not be obtained) the analyses using the **FASM, ITT and PP populations** will use the following approach:

Baseline Mucus Score	Post-Baseline Mucus Score	Mucus Score Used in Analysis
0-4	Too thick to collect	Score equal to baseline
>4	Too thick to collect	Post-baseline score =4
Too thick to collect	Any observed mucus score	Baseline score =0
Too thick to collect	Too thick to collect	Change from baseline = 0

A sensitivity analysis using the FASM population will also be done and if the cervical mucus was too thick to be collected (and thus a cervical mucus score could not be obtained) the mucus score will be assigned using multiple imputation.

The SAS code for the 2 primary contrasts of interest are:

```
PROC MIXED DATA=MUCUS;
CLASS VISIT PERIOD INTERVENTION SEQUENCE;
MODEL MUCUS_CHG = PERIOD INTERVENTION VISIT SEQUENCE / S;
RANDOM SUBJ_ID;
REPEATED / SUBJECT=SUBJ_ID*PERIOD;
ESTIMATE 'EFFECT OF INFRINGEMENT' INTERVENTION 1 -1 ;
ESTIMATE 'EFFECT OF TIME' VISIT 1 -1 1 -1;
RUN;
```

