## 3.0 STATISTICAL METHODS

### 3.1 Statistical Handling Policy and Analysis Conventions

This section details general policies to be used for the statistical analyses. Departures from these general policies may be given in the specific detailed sections of this SAP. When this situation occurs, the rules set forth in the specific section take precedence over the general policies. The following policies will be applied to all data presentations and analyses.

- All statistical tests will use a significance level of  $\alpha = 0.05$ . Two-tailed tests will be performed for all analyses that use statistical testing.
- All p-values will be rounded to 3 decimal places. All p-values that round to 0.000 will be presented as '<0.001' and p-values that round to 1.000 will be presented as '>0.999'. Any

p-value  $\leq 0.05$  will be considered statistically significant and will be marked with one asterisk (e.g., 0.025\*).

- Summary statistics will consist of the number and percentage of responses in each category for discrete variables, and the mean, median, standard deviation (SD), minimum, and maximum for continuous variables.
- All mean values will be formatted to one more decimal place than the measured value. Standard deviation values will be formatted to two more decimal places than the measured value. Median values will be formatted to same decimal place as the measured values when that is possible without losing accuracy; otherwise, they will be formatted to one more decimal place than the measured values.
- All percentages will be rounded to one decimal place. The number and percentage of responses will be presented in the form XX (XX.X), where the percentage is in the parentheses. The denominator for percentage calculations will be the number of non-missing observations.
- All listings will be sorted for presentation in order of site number, subject number, and date of procedure or event.
- All analysis and summary tables will have the population sample size (n and % (% will not be shown in the column header if the table also presents means)) for each treatment group in the column heading.
- Calculating change from baseline to a visit will be done as follows: Change = Visit – Baseline.
- Baseline is defined as the last data point before the day of infringement (i.e. V2R-1 or V3R-1).
- Version 9.4 of SAS® or higher will be the statistical software package used to produce all summaries, listings, statistical analyses, and graphs.

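### The primary mixed model analyses change in mucus score without the period baseline as covariate, so the missed-versus-delayed contrast carries avoidable baseline error

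*SAP*

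**What the plan says.** SAP section 3.7.1 sets up a "mixed model for repeated measures using as response delta to" the day of infringement and the day after, in periods 2 and 3. That gives four changes per woman, two in each period. Section 3.1 defines the reference value: "Baseline is defined as the last data point before the day of infringement", so each period has its own single baseline.

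The model terms are given twice. The text reads "The covariates will be the period (or period effect), the intervention (type of infringement: missed pill or delayed pill"), followed by sequence, time and a random subject effect. The code reads "MODEL MUCUS_CHG = PERIOD INTERVENTION VISIT SEQUENCE / S". The baseline score appears in neither. The planned sensitivity analyses change the population (ITT, PP) or the handling of mucus too thick to collect; none adds baseline.

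The primary test "will be the significance of the overall mean (intercept"). Missed versus delayed pill is estimated by "ESTIMATE 'EFFECT OF INFRINGEMENT' INTERVENTION 1 -1", one of the two contrasts for which the SAP supplies code, and a positive result is to be read as a signal of effect.

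**The concern.** Analysing raw change fixes the coefficient of baseline at 1. When the true within-woman slope of the later score on baseline differs from 1, the baseline's own error is added to the response. The baseline is specific to the period, so that error goes with the same sign into both changes of the period and stays in the difference between periods. A random subject effect removes what is common to both periods, and this error is not.

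The SAP's rules for uncollectable mucus tie change to baseline further. Take two women whose mucus is too thick after infringement. A baseline of 3 gives a change of 0. A baseline of 10 has its later score set to 4, a change of -6. The outcome category is the same, and the two changes differ only through baseline.

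At stake is the precision of a named contrast in a study planned for 45 completers. Section 2.5 prefers the quantitative score because it expects that analysis to have the most power, yet states that nothing published allows it to be sized.

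**Working it through.** **The plan's own figures.** Section 2.5 states power of 79.1% (difference 14%, discordance 17%) and 82.4% (15%, 18%) for paired proportions in 45 women. An exact unconditional test reproduces both at one-sided 0.05. At the two-sided 0.05 of section 3.1 it gives 69.5% and 73.6%, which is a separate matter. No power, variance or correlation is given for the mixed model, so everything below rests on assumed values.

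**Set-up.** Remove the subject effect, which cancels in missed minus delayed. Within a period, let each post-infringement score have variance 1, let the baseline have SD k relative to that, and let every pair of scores have correlation rho. The contrast uses the mean of the two post-infringement scores.

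- Variance of that mean: (1 + rho)/2
- Its covariance with baseline: rho × k
- Per-period variance of raw change: (1 + rho)/2 + k² − 2 × rho × k
- Per-period variance after adjustment: (1 + rho)/2 − rho²

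The ratio of the last two is the adjusted-to-unadjusted variance of the contrast.

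**Equal variances (k = 1).** Raw change gives 1.5(1 − rho), adjusted gives (1 − rho)(1 + 2 rho)/2, and the ratio is (1 + 2 rho)/3.

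- rho 0.2: 0.56/1.20 = 0.47; SE falls 32%; equivalent to 45/0.467 = 96 women unadjusted
- rho 0.6: 0.44/0.60 = 0.73; SE falls 14%; 45/0.733 = 61 women
- rho 0.9: 0.14/0.15 = 0.93; SE falls 3%

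**Baseline SD half the post-infringement SD (k = 0.5).** This is plausible if baselines cluster near the floor of 0.

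- rho 0.2: 0.56/0.65 = 0.86; SE falls 7%; 52 women
- rho 0.5: 0.50/0.50 = 1.00; no gain, because the slope rho/k is exactly 1
- rho 0.6: 0.44/0.45 = 0.98; SE falls 1%; 46 women

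**Simulation (k = 1, 45 women, 4,000 runs).** For rho 0, 0.3, 0.5, 0.7 and 0.9 the formula gives 0.33, 0.53, 0.67, 0.80 and 0.93. The simulated ratios were 0.35, 0.54, 0.69, 0.82 and 0.95. With scores rounded and clipped to 0–12 they were 0.34, 0.55, 0.68, 0.83 and 0.98. The mean estimated contrast was practically the same with and without adjustment. The small excess over the formula is consistent with the cost of estimating a slope.

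**What is not affected.** The visit contrast compares two changes in the same period, which subtract the same baseline, so the baseline cancels. The overall mean change keeps its estimate if the covariate is centred.

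**The case against.** The strongest reply is that change from baseline is the stated endpoint, that a mixed model of change is valid, and that nothing in the SAP is contradicted. The study describes itself as exploratory, the contrast is a supporting one, and the gain may be nil. All of this is true. It limits the weight of the point without removing it, because the covariate is already measured.

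A reader might infer that a chance difference between period baselines biases the contrast through regression to the mean. The SAP does not support that. The order of delayed and missed pill is randomised (section 2.3) and each baseline precedes its infringement (section 3.1). A realised imbalance shifts one estimate, but over randomisation the shifts average to zero; they are variance and are already counted above. Nor may one infer that the primary intercept test is weakened.

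A practical objection stands. When baseline and later mucus are both too thick, the SAP fixes only the change, at 0, and assigns no baseline score. With a covariate added, PROC MIXED would drop those rows, which are exactly the no-change observations. The fix must therefore state a baseline value. Women with data in only one of periods 2 and 3, whom the FASM admits, add nothing to the within-woman term, but they do no harm.

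Finally, one linear slope only approximates a bounded score with imputed values. In the simulation with rounding and clipping the gain remained.

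**Conclusion.** The point holds as an avoidable loss of precision in the missed-versus-delayed contrast. Over an assumed rho of 0.2 to 0.6, the variance ratio runs from 0.47 to 0.73 with equal variances. With a baseline SD half as large it is 0.86 and 0.98 at the two ends and 1.00 at rho 0.5. These figures assume one common correlation for all pairs of scores in a period, a linear relation, both periods observed, and subject fitted as a random effect as the text describes. Because the SAP gives none of these quantities, the gain can be called neither large nor small in advance. There is no bias, and the primary test of overall mean change is untouched.

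**What to change.** In section 3.7.1, for the missed-versus-delayed contrast only:

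1. Add the R-1 mucus score to the MODEL statement as two terms: the woman's mean baseline over periods 2 and 3, centred at the overall mean, and the period's deviation from that woman's mean. Two terms keep one slope from mixing between-woman and within-woman relations.
2. State that the baseline covariate is 0 whenever baseline mucus is too thick to collect, including when the later sample is too thick as well, with the change kept at 0. This extends the SAP's existing baseline rule, and no zero-change rows are lost.
3. Keep the unadjusted model for the test of overall mean change, and say which model serves which question.

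The cost is two model terms, one sentence on the covariate value and a second model run. No new data are needed. The price in the analysis is a little information spent on estimating the slope, which matters only where the true gain is near nil.

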### 2.2 Objectives

The primary objectives of the study are:

- to determine the effect of a delayed intake of 6 hours or of a missed pill on cervical mucus score compared to cervical mucus score during reported perfect daily use of norgestrel 75 mcg
- to estimate the duration of the protective effect of cervical mucus after last pill intake of norgestrel 75 mcg during reported perfect use (The protective effect of cervical mucus is considered as present when the score is below or equal 4.)

---

 defined as the day before the delayed intake or the missed pill

The secondary objectives of the study are:

[figure not shown]
- to evaluate and compare the percentage of subjects with a protective cervical mucus score during reported perfect daily use of norgestrel 75 mcg, during a treatment period with a delayed intake of 6 hours and during a treatment period with a missed pill of norgestrel 75 mcg.
- to evaluate and compare the ovarian activity during reported perfect daily use, during a treatment period with a delayed intake of 6 hours and during a treatment period with a missed pill of norgestrel 75 mcg.
- to assess if a combination of cervical mucus score and ovarian status can be considered as a measure of protection from conception during reported perfect daily use, during a treatment period with a delayed intake of 6 hours and during a treatment period with a missed pill of norgestrel 75 mcg.
- to determine levonorgestrel pharmacokinetics after a single dose of norgestrel 75 mcg, at steady state, after a delayed intake and after a missed pill.
- to assess the safety of norgestrel 75 mcg taken daily for 12 weeks.

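### The primary test is tied to the model intercept, which is one reference cell and not the overall mean, and the printed PROC MIXED step does not fit the model described in the text

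*SAP*

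**What the plan says.** Section 3.7.1 of the SAP describes a mixed model for four changes from baseline per woman: day of infringement (R) and day after (R+1), in periods 2 and 3. The primary test "will be the significance of the overall mean (intercept"). The SAP then asks whether the overall mean change differs from zero, whatever the type of infringement. On coding it says: "Time, period intervention type, and sequence will be considered as categorical variables". The subject is to be a random effect, with a repeated time effect within subject-by-period and a covariance structure chosen "using the best fit among unstructured matrix (UN) compound symmetry (CS) and autoregressive structure".

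The code is introduced with "The SAS code for the 2 primary contrasts of interest are". It contains "CLASS VISIT PERIOD INTERVENTION SEQUENCE", a RANDOM statement for the subject identifier, "REPEATED / SUBJECT=SUBJ_ID*PERIOD", an ESTIMATE for infringement type, and "ESTIMATE 'EFFECT OF TIME' VISIT 1 -1 1 -1". It has no ESTIMATE for the overall mean.

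**The concern.** The overall mean and the intercept are treated as one quantity. With CLASS factors, PROC MIXED sets the last level of each factor to zero, so the intercept is the fitted mean in a single cell. It equals the overall mean only by coincidence or under sum-to-zero coding, which the SAP does not specify. A programmer who follows the bracketed word, or who reads the solution table that the S option prints, would report a p-value for one cell as the primary result. Which cell that is depends on how the labels sort.

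The printed step also fits a different covariance model from the one in the text. A subject identifier that is absent from CLASS becomes a single random slope on the ID number if it is numeric, and stops the step if it is character. With no TYPE=, the residuals are independent.

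A lesser matter: section 2.2 sets out "to determine the effect of a delayed intake of 6 hours or of a missed pill on cervical mucus score", but the model has no infringement-by-time term. It therefore gives no mean change for each type at R and at R+1.

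**Working it through.** **Inputs.** From the SAP: 45 completers (2.5), two-sided 0.05 (3.1), the cross-over layout (2.3), and the factors and four-coefficient VISIT estimate in 3.7.1. Assumed: 23 women in arm A and 22 in arm B; 'last' means period 3, visit R+1, arm B. Section 2.5 states that no variance or covariance data exist, so there is no planned figure for this test to reproduce; its power figures concern paired proportions.

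**What the intercept is.** With four VISIT levels nested in period, the fixed-effects design has rank 6. The default intercept is the fitted value for period 3, R+1, arm B and whichever infringement label sorts last. If 'Missed' sorts last, that cell is empty: arm B has the delayed intake in period 3. Half of the 16 possible reference cells are empty in the same way.

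**Example 1.** Delay has no effect; the missed pill gives +0.5 at R and +1.0 at R+1.
- Overall mean = (0 + 0 + 0.5 + 1.0)/4 = 0.375.
- In period 3 the missed pill belongs to arm A, so the fitted rise from R to R+1 is 0.5 × 23/45 = 0.256, and half of it is 0.128.
- Intercept with 'Missed' last: 0.75 + 0.128 = 0.878. With 'Delayed' last: 0 + 0.128 = 0.128.

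**Example 2.** Both types +1 at R and 0 at R+1: overall mean 0.5, intercept 0.

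**Power at a true overall mean of 0.25 SD.** Assumed correlations between changes, within/between periods (w/b): 0.5/0, 0.5/0.25, 0.7/0.5. For the overall mean, Var = [(1 + w + 2b)/4] × ¼(1/23 + 1/22), in SD² units. The SEs are 0.091, 0.105 and 0.122. Intercept SEs from generalized least squares are 0.197 to 0.205. Power uses the true covariance and a normal approximation.

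| Test and true pattern | 0.5/0 | 0.5/0.25 | 0.7/0.5 |
|---|---|---|---|
| Overall mean, any pattern | 78% | 66% | 53% |
| Intercept, uniform shift | 24% | 24% | 23% |
| Intercept, both types rise at R only | 5% | 5% | 5% |
| Intercept, missed pill only (+1/3, +2/3), 'Missed' last | 84% | 84% | 82% |
| Same data, 'Delayed' last | 7% | 7% | 7% |

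With t on 43 df, the overall-mean test has 76/64/51%.

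**Printed code under a true null, nominal 5%.**
- Numeric IDs 1 to 45, ID slope fitted by REML: the intercept rejects 9/11/14%. An overall-mean estimate added to the same step would reject 14/21/30%.
- Independent errors without the ID slope: intercept 7/7/8%, overall mean about 11/16/23%, time contrast under 1%.
- A separate simulation of the printed step, with intra-subject correlation from 0 to 0.7, gave 5.6% to 17.9% for the intercept and 6.9% to 34.2% for an overall-mean contrast. With the subject properly classified, that contrast stayed at 5.0 to 5.7%.

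**Time contrast.** The R+1 score is taken 24 − 6 − 0.5 = 17.5 h after a delayed pill, but 48 − 0.5 = 47.5 h after the last pill when one is missed. The contrast pools the two. With delay +1 then 0 and missed +1 then +2 (illustrative), it returns exactly 0. Its coefficients also give the sum of the two within-period differences, not their average.

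**The case against.** The intended quantity is not in doubt: the SAP names the overall mean, puts the intercept only in brackets, and asks for a pooled answer. The code is headed as serving the two contrasts only. The text already requires a random subject effect and a chosen covariance structure, and a final TYPE= cannot be printed before that choice is made. A character ID would stop the step and reveal the fault. The study is declared exploratory.

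Much of this is fair, and it limits the harm. The label-order figures apply only if the intercept row is actually reported. The inflated rejection rates need a numeric ID and uncorrected code, and those for the overall mean describe an estimate that nobody has coded. The infringement-by-time term is a preference. The 5% shown for the corrected test comes from a per-woman t test and a simulation, not from the full step with a selected structure. If default containment df (about 132) were used for a statistic with 43 true df, it would reject about 5.4%.

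The core is untouched. The sentence that defines the primary test equates two different quantities, and the plan gives no coefficients for the one it wants.

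**Conclusion.** The concern holds and must be fixed before analysis. As written, the quantity named for the primary test is a label-dependent cell mean, and the only model code contradicts the text on the subject effect and the covariance. The intercept's standard error is 1.7 to 2.2 times that of the overall mean under the assumed correlations. Its estimate can be more than double the overall mean, a third of it, or zero. The direction of the error cannot be predicted without knowing the labels and the pattern of effect. That the intercept is a reference cell follows from the coding alone. The sizes rest on assumed effects and correlations, a 23/22 split and complete data.

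**What to change.** In section 3.7.1, replace the bracketed intercept by the equally weighted overall mean, estimated by an explicit contrast. In the code:

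- Recode VISIT as a two-level TIME (R, R+1), and use TIME in MODEL.
- `CLASS SUBJ_ID TIME PERIOD INTERVENTION SEQUENCE;`
- Keep the RANDOM statement, and write `REPEATED TIME / SUBJECT=SUBJ_ID*PERIOD TYPE=<selected>;`. With two times per block, CS and AR(1) are the same model, so the choice is UN or CS. State the selection criterion and the degrees-of-freedom method.
- `ESTIMATE 'OVERALL MEAN' INTERCEPT 1 PERIOD .5 .5 SEQUENCE .5 .5 INTERVENTION .5 .5 TIME .5 .5;` as the primary test.
- Change the time contrast to `TIME 1 -1`.

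Recommended but not required: add `INTERVENTION*TIME` (with .25 .25 .25 .25 in the overall-mean ESTIMATE) and `LSMEANS INTERVENTION*TIME / CL`, and read the time effect within each infringement type. The overall-mean ESTIMATE is estimable with and without the interaction, and returns 0.375 in example 1 both ways.

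Cost: one phrase, four edited code lines (CLASS, MODEL, REPEATED, time contrast), one new line, and four cell means in Table 14.2.1 if the recommendation is taken. No new data are needed.
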